- Adult ADHD Self Report Scale (ASRS) for ADHD symptoms³⁴ (4 mins) is an 18 question assessment for presence and severity of ADHD symptoms by self-report.

Quality of Life: WHOQOL-Bref³⁵ (5 mins) is a well validated and widely used scale for persons with substance use disorders that measures the quality of social and occupational functioning as well as other domains.

Medical/Infectious Disease Questionnaire: This form documents the completion of antimicrobial therapy and re-hospitalization for infection. The initial evaluation documents the relevant infection and medical details such as infection site, organism, and stage. It also extracts the type of anti-infective, route of administration, dose, planned duration and, at select sites, knowledge of, experience with, and attitudes related to HIV Pre-Exposure Prophylaxis (PrEP). Information collected on follow-up will be alteration of treatment plan, infection related adverse events (e.g. PICC complications, drug reaction/toxicity to anti-infective agent prescribed by non-study clinicians, etc), intervening hospitalizations, and questions related to PrEP. Current study participants, at select sites, who are beyond the hospital-discharge timepoint will be asked these PrEP questions retrospectively, at one timepoint, at the next scheduled study follow-up visit.

Severity Scoring: The Elixhauser Comorbidity Index³⁶ is a validated scoring index for predicting mortality based on patient comorbidity. This will be performed via chart review.

Substance Use Treatment (SUTx) Form: This questionnaire documents the details of MOUD and substance use treatment history in the intervention and TAU arms. For those participants receiving LAB, it documents date of administration, dose, location and prescribing provider. The TAU section of the questionnaire queries the variety of different forms a substance use treatment that participants may or may not receive in the community. This includes MOUD (buprenorphine, extended-release naltrexone, or methadone) prescribed by non-study related physicians, behavioral therapy (i.e. 12 step

programs), and whether participants have enrolled in a community opioid treatment program (OTP).

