12.0 Data Management

Power Analysis: Previous studies of buprenorphine initiation in an Emergency Department⁴² and on a medical inpatient service,⁴³ yielded rates of post-discharge buprenorphine maintenance treatment in the 70% range. The Emergency Department study implemented a Screening, Brief Intervention and Referral control condition, similar to the TAU condition planned in the current protocol, which yielded a rate of post-discharge buprenorphine maintenance treatment of 45%. We anticipate that the population recruited for this study will be among the most severely ill patients with OUD, being those requiring hospitalization for infections, and therefore we conservatively assume that the proportion of patients meeting our primary outcome (enrolled in MOUD 12 weeks after hospital discharge) will be 40% in the TAU arm and 60% in ID/LAB arm. We have chosen a sample size of N = 200 total (N = 100 per study arm), in order to ensure sufficient power (power = 80%) with a two-sided level of significance of 5% to detect a difference of at least 19.7% between the TAU and ID/LAB treatment groups (i.e., 40% treatment enrollment in the TAU arm and at least 59.7% treatment enrollment in the ID/LAB arm). This rate difference of 19.7% is equivalent to an odds-ratio of 2.2 and would be clinically meaningful.

Data Analysis Plan:

Primary outcome: The primary outcome will be a binary indicator of whether a patient is enrolled in and receiving effective MOUD (buprenorphine, methadone, or injection naltrexone) at 12 weeks (3 months) after randomization.

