Secondary outcomes: 1) Days using opioids, and days injecting drugs per 28 days prior to each major assessment point (weeks 4, 8, 12, and 24 post randomization) (longitudinal, continuous); 2) Urine toxicology-confirmed abstinent (urine toxicology negative for illicit opioids, and self-report negative over past 7 (at week 1) or 30 days (weeks 4, 8, 12, 24) (longitudinal, binary); 3) Completion of the prescribed course of antimicrobial therapy (binary), Re-hospitalization for infection by week 12 (binary); 4) Days using other drugs/alcohol per 28 days prior to each assessment (longitudinal, continuous); 5) Urine toxicology positive for non-opioid drugs (longitudinal, binary); 6) Social functioning and quality of life (WHOQOL-Bref) at 12 and 24 weeks after randomization (longitudinal, continuous); 7) Modified PEG Pain Scale at each assessment (Longitudinal, continuous) 8) HIV risk behaviors—days in past 28 days of vaginal or anal sex without a condom at weeks 4, 8, 12, 24 (longitudinal, continuous); 8) Any needle sharing in past 28 days (longitudinal, binary); 9) Treatment satisfaction (via the TSR)¹² at 12 and 24 weeks (longitudinal, continuous); 10) Discharge “against medical advice” (binary); 11) Cure of index infection (binary); 12) HCV cure or link to treatment (binary); 13) HIV Viral suppression (Viral Load < 200 copies), if HIV positive (binary); 14) overall hospitalization by week 12; 15) ED visits by week 12; 16) Serious adverse events (SAFETEE and non-fatal and fatal overdose) (binary).

Additional variables: *Covariates, primary and secondary analyses: Stratification factors:* Site (3 sites: YNHH; Columbia/Penn State Hershey; South Carolina/Greenville) will be included as a fixed effect in all analyses. *Covariates:* In general, the baseline score for each outcome measure (where applicable) will be included as a covariate in outcome analyses. *Moderators:* A range of baseline moderator variables will be explored including 1) Demographic characteristics (gender, age, ethnicity, living situation (domiciled vs homeless); 2) Modified Pain PEG scores at baseline (continuous) 3) Evidence of fentanyl use at admission (urine toxicology, self-report) (binary); 4) Other substance use at baseline (any cannabis, any stimulant, any heavy drinking days; binary); 5) Probable major depression at baseline (binary based on PHQ score); 5) Type of infection (endocarditis/ osteomyelitis/bacteremia/ cellulitis/ etc.). *Mediators:* 1) Social functioning

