(WHOQOL-Bref); continuous); 2) Opioid craving (continuous); 3) Pain (Modified PEG scores; continuous).

Intent to Treat, Dropouts, and Missing Data: All analyses will be on the Intent-to-treat (ITT) sample, i.e., all randomized subjects (N=200) according to the treatment arm to which they were assigned. For the primary outcome and secondary outcomes related to treatment engagement, any patients lost to follow-up will be assumed not to be enrolled in treatment nor to have completed the antimicrobial course. Loss to follow-up will be minimized through collection of extensive locator information at baseline and proactive outreach, as described above. For the secondary outcomes related to substance use, missing data (patients who cannot be located) will be assumed to be opioid positive (not abstinent), a typical assumption which is reasonable based on the high rate of relapse among patients with OUD who discontinue medication treatment.^{14,44-46} For other secondary outcomes, missing data will be treated as missing at random. Longitudinal mixed effects models do not require complete data to provide estimates of the outcome, and the estimates are considered valid under the assumption that the data are missing at random.⁴⁷ We will additionally perform sensitivity analysis for the secondary outcomes to examine the influence on the outcomes of dropout and missing data by performing several imputation methods, for instance imputing missing weeks as all abstinent or all non-abstinent. Comparison of the inferences from assuming various models for the missingness provides a measure of the validity of the efficacy estimate from the initial model.

Significance Testing and Preliminary Analyses: All tests for main effects will be performed at two-sided significance level of 5%. Before performing specific analyses, we will examine the distributions of outcome measures and covariates and investigate for outliers. The distributions of continuous variables will be checked for normality, and transformed, if necessary. Distribution of demographic and other baseline variables will be examined and described in terms of means, standard deviations, proportions and 95% confidence intervals. Covariates will be examined for association with treatment outcome. Covariates associated with treatment outcome will be adjusted for in models used to test study hypotheses.

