Secondary outcomes: Statistical Models: For each of the secondary outcomes (see above) the effect of randomization to the ID/LAB arm compared to the TAU arm will be estimated with a model of the same general form as for the primary outcome (independent variables: treatment assignment (ID/LAB vs TAU), Site as a fixed effect, and baseline score as covariate where relevant) using logistic regression models (for binary outcomes), generalized linear model (for continuous outcomes), or longitudinal generalized mixed effects model (for longitudinal outcomes) with appropriate link functions (e.g. logit for binary outcomes). Longitudinal outcomes analyzed using a mixed effects models will utilize a generalized estimating equation with an autoregressive correlation structure (AR(1)) to account for within subject correlation over time, as well a random intercept accounting for between subject variability. In addition to site, covariates that are found to be related to the outcomes will be added to the models to improve the power for detecting significant differences.

Moderation and Mediation: Moderation Statistical Models: The effect of randomization to the ID/LAB vs TAU arms will be estimated for subpopulations based on the demographic and baseline characteristics selected as moderators (see above). We will estimate the moderation effect on primary outcome using a similar model to Aim 1 primary outcome with the inclusion of moderator by treatment interaction: $Y_i = \beta_0 + \beta_1 Trx_i + \beta_2 M_i + \beta_3 Trx_i M_i + \beta_4 C_i + s_i$ where M_i is the moderator status for i^{th} subject and Trx_i is subject's treatment assignment. Regardless of the significance of the interaction term, we will use the model to estimate the 95% confidence interval of the treatment effect for each level or category of the moderator variable, or the treatment effect at selected values of the moderator variable, if continuous. The moderator analyses are exploratory and hypothesis generating, but significant moderator effects can be useful in planning future efforts at implementation of medication treatment for opioid use disorder in medical settings by identifying subgroups that may particularly benefit. Identifying subgroups where there is less benefit may suggest future modifications to the implementation strategy to achieve better effect in those subgroups.

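### Re-hospitalization for infection by week 12 needs an analysis that uses partial follow-up; logistic regression under a general missing-at-random rule cannot

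*Combined protocol and SAP*

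**What the plan says.** All of this is in the combined protocol and SAP.

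- **Outcome.** Section 12.0, secondary outcome 3, lists "Re-hospitalization for infection by week 12 (binary" in its label. Items 14 and 15 read "14) overall hospitalization by week 12; 15) ED visits by week 12" and carry no variable type.
- **Model.** Section 12.0, statistical models for secondary outcomes, estimates the arm effect "using logistic regression models (for binary outcomes", with site as a fixed effect. No censoring, offset or time-to-event method appears.
- **Missing data.** Section 12.0 gives fixed-value rules for treatment engagement, for completion of antimicrobials and for substance use. Readmission is in none of these groups, so the remaining rule applies: "For other secondary outcomes, missing data will be treated as missing at random". The sentence that supports this rule is about longitudinal mixed models. Sensitivity analyses by several imputation methods are promised for the secondary outcomes, and the one example imputes weeks as abstinent or not.
- **Analysis set.** All analyses use all 200 randomized patients.
- **Data source.** On the Medical/Infectious Disease Questionnaire, section 10.0 says: "This form documents the completion of antimicrobial therapy and re-hospitalization for infection". Section 10.0 schedules it at baseline and at weeks 4, 8, 12 and 24. The description mentions hospitalizations between visits but not emergency visits.

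**The concern.** A cumulative outcome becomes known at different times depending on its value. A patient readmitted in week 3 and then lost is a settled yes. A patient without readmission at week 4 and then lost is undetermined for the other eight weeks. Logistic regression needs one completed value per patient, so the analyst must decide what to do with the second patient, and the plan gives no rule.

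The mixed-model argument does not help. Those models use the repeated measurements that a patient did provide, and here there is only one value. If only the undetermined patients are set to missing, missingness depends on the outcome by construction.

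Readmission is one of the health-care-use outcomes of Aim 3. If loss differs between arms, the choice of coding can create a difference where there is none, and the two obvious codings push it in opposite directions. Unequal loss is possible: section 10.0 and the study schedule give only ID/LAB patients study injections, scheduled at weeks 4 and 8, which is an extra reason to attend. It is not established, because section 10.0 also has the nurse care manager follow TAU patients on a similar schedule.

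**Working it through.** **The plan's own figure.** Section 12.0 sizes the trial on the primary outcome: "40% treatment enrollment in the TAU arm and at least 59.7% treatment enrollment in the ID/LAB arm", 100 per arm, 80% power, two-sided 5%. With mean proportion 0.4985, n = [1.96·√(2·0.4985·0.5015) + 0.8416·√(0.40·0.60 + 0.597·0.403)]² / 0.197² = 99.9, so 100 per arm. The odds ratio is (0.597/0.403)/(0.40/0.60) = 2.22. Both reproduce. The plan gives no figure for readmission.

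**Inputs.** From the documents: 100 per arm, two-sided 5%, a 12-week window. Assumed, because the documents give no event or loss rate: true 12-week risk p = 0.30, constant hazard, proportion L lost, loss time uniform over 12 weeks and independent of readmission.

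**Step 1. Share of lost patients with a known event.** λ = −ln(1 − 0.30)/12 = 0.0297 per week. Then q = 1 − p/(12λ) = 1 − 0.30/0.3567 = 0.159.

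**Step 2. Expected rate under each handling.**

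- (a) Lost without a known event coded no: (1 − L)p + Lq. At L = 0.30: 0.210 + 0.048 = 0.258.
- (b) Known events kept, event-free lost patients dropped: the same numerator over (1 − L) + Lq. At L = 0.30: 0.258/0.748 = 0.345.
- (c) All lost patients excluded, including those with a known event: p = 0.300.
- (d) Kaplan-Meier or life table: 0.300, confirmed by simulation.

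| Loss | (a) coded no | (b) event-free lost dropped | (c) all lost excluded |
|---|---|---|---|
| 10% | 28.6% | 31.2% | 30.0% |
| 20% | 27.2% | 32.7% | 30.0% |
| 30% | 25.8% | 34.5% | 30.0% |
| 40% | 24.4% | 36.7% | 30.0% |

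If last contact is instead at week 1, 4 or 8 with equal chance, q = 0.118, and 30% loss gives 24.5% under (a) and 33.4% under (b). Over true risks of 20 to 40% and losses of 10 to 40%, that timing makes (a) 1.2 to 9.5 points too low and (b) 0.7 to 5.9 points too high.

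**Step 3. Arm comparison with equal loss.** With true rates of 40% and 25% (odds ratio 0.50), 30% loss in both arms and last contact at week 1, 4 or 8, the odds ratio is 0.52 under (a), 0.50 under (b) and 0.50 under (c). The comparison hardly moves.

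**Step 4. Arm comparison with unequal loss and no true effect.** Risk 30% in both arms; loss 10% in ID/LAB and 30% in TAU; uniform loss times.

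- (a) 28.59% − 25.77% = +2.8 points. The pooled standard error is √(2·0.2718·0.7282/100) = 6.29 points, so the shift is 0.45 standard errors. Rejection probability is about Φ(0.45 − 1.96) + Φ(−0.45 − 1.96) = 7.3%.
- (b) 31.21% − 34.46% = −3.2 points, with about 91.6 and 74.8 patients left. The standard error is 7.31 points, the shift 0.44 standard errors, and rejection again about 7.3%.

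With last contact at week 1, 4 or 8 the differences are +3.6 and −2.5 points, and rejection is 9.0% and 6.3%. At 10% versus 40% loss and uniform times they are +4.2 and −5.5 points.

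**Step 5. Cost of excluding all lost patients.** At 10% versus 30% loss, the standard error of the risk difference under (c) is √(0.21/90 + 0.21/70) = 7.3 points. Kaplan-Meier with Greenwood's variance gives 6.9 points. The variance under (c) is larger by (7.3/6.9)² − 1, about 12%.

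**The case against.** A reader might infer that the planned analysis is biased even when dropout is purely random, and for all three event outcomes. The documents do not support that.

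- Bias depends on the coding. Excluding every lost patient is unbiased under random loss, and so is imputation that uses the time observed. The plan names no coding, so no bias is shown.
- Coding lost patients as event-free is not a missing-at-random rule. An analyst might still adopt it to keep all 200 patients in the model.
- Only infection re-hospitalization is labelled binary. Overall hospitalization and ED visits have no type, and ED visits could be a count.
- Observation may not stop at the last visit before week 12. Section 10.0 repeats the questionnaire at week 24 and allows telephone and field interviews, section 14.0 describes community tracing, and Appendix A allows chart review for this form. These could recover some gaps. The chart review, however, is described only for remote inpatient assessment, and verification from treatment programs, prescription monitoring or the EMR is specified only for the primary outcome.
- Sensitivity analyses are promised, but the only example does not fit readmission.
- The sizes are modest. A false difference of 3 points is about half of the 6.5-point standard error at full follow-up, √(2·0.30·0.70/100), and it needs clearly unequal loss.

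Each of these stands and limits the point. None supplies a method that uses partial follow-up, or a justification of the missing-data rule that fits a single binary value.

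**Conclusion.** The point holds for infection re-hospitalization. A cumulative yes/no outcome, observed for different lengths of time, is assigned to a model that cannot use partial follow-up, under a rule whose stated support does not apply to it. Two natural codings misstate the rate in opposite directions: 25.8% and 34.5% against a true 30% at 30% random loss. The third, excluding all lost patients, is unbiased under random loss but discards observed readmissions, has about 12% more variance than Kaplan-Meier at 10% versus 30% loss, and departs from the all-randomized rule.

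For the arm comparison the risk is mainly unequal loss. At 10% versus 30%, the false difference is about 3 points in either direction and the type I error between 7 and 8% with uniform loss times (6 to 9% over the two loss timings examined). Equal random loss leaves the odds ratio nearly unchanged.

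These figures rest on assumed event and loss rates, a constant hazard and loss unrelated to readmission. They ignore death and the index stay. The outcome is secondary, and the primary analysis is not touched.

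**What to change.** In section 12.0, make time to first event the main analysis of infection re-hospitalization:

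- Measure time from randomization. Censor at week 12 or, if earlier, at the last date to which events were ascertained. Any later interview, including week 24, or a records check may set that date.
- Treat death as a competing event. Patients are randomized as inpatients, so count only admissions after discharge from the index stay.
- Report the 12-week cumulative incidence per arm, the risk difference with its 95% confidence interval, and a site-stratified test.
- State that, for this outcome, the missing-at-random rule means independent censoring.
- Keep the logistic model as a sensitivity analysis, with the handling of lost patients with and without a known event written down.

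State the variable type and data source of overall hospitalization and ED visits. If they are analysed as yes/no outcomes, apply the same method to overall hospitalization and first ED visit.

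The cost is SAP wording, one more model, and recording event dates and last-ascertainment dates. The method relies on independent censoring, so it does not cure loss that is related to readmission. It also reports a risk difference in place of an odds ratio.

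### For the Aim 2 abstinence outcome, the two example missing-data scenarios add only one new analysis, and neither lets missing patients differ between arms, so the pair can miss a reversal

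*Combined protocol and SAP*

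**What the plan says.** The relevant text is in section 12.0 of the combined protocol and SAP.

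- **Outcome** (Secondary outcomes, item 2): "Urine toxicology-confirmed abstinent (urine toxicology negative for illicit opioids, and self-report negative over past 7 (at week 1) or 30 days" at the later visits, a longitudinal binary measure. It serves Aim 2.
- **Main rule for substance-use outcomes** (Intent to Treat, Dropouts, and Missing Data): "missing data (patients who cannot be located) will be assumed to be opioid positive (not abstinent").
- **Sensitivity analysis for the secondary outcomes** (same paragraph): several imputation methods are promised, "for instance imputing missing weeks as all abstinent or all non-abstinent".
- **Purpose given for it**: "Comparison of the inferences from assuming various models for the missingness provides a measure of the validity of the efficacy estimate from the initial model".
- **Model** (Secondary outcomes: Statistical Models): longitudinal models "with appropriate link functions (e.g. logit for binary outcomes").

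The plan states no expected loss to follow-up and does not assume that loss is equal between arms. It names no analysis in which missing patients in the two arms are given different outcomes.

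**The concern.** The comparison of missingness models is offered as evidence on whether the efficacy estimate can be trusted. For that, the models compared should cover the ways in which missing data could mislead. The main one is that missing patients in one arm fared differently from missing patients in the other.

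Such a difference is plausible here, in either direction. Section 2.0 describes the ID/LAB depot as giving therapeutic blood levels for a month. Sections 7.0 and 10.0 describe TAU as ranging from detoxification to consult-led start of medication. A patient lost from one arm need not resemble a patient lost from the other.

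For abstinence, one example repeats the main analysis and the other treats missing patients in both arms alike. If only these two were run, agreement between them would say nothing about that difference. What is at stake is how firmly an Aim 2 abstinence result can be stated; section 4.0 treats the opioid outcomes as key secondary outcomes. The primary outcome has its own rule and is not affected.

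**Working it through.** **Inputs.** From the plan: "N = 200 total (N = 100 per study arm"), two-sided 5% level, and the two imputation examples. Assumed, because the documents give neither: abstinence rates among observed patients, and loss rates. The 60% v 40% illustration borrows the rates that the power analysis uses for the primary outcome.

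**The plan's own figure.** None is given for the missing-data check. The power statement reproduces: 40% v 59.7% with 100 per arm gives power 0.800, and the odds ratio is (0.597/0.403)/(0.40/0.60) = 2.22, stated as 2.2.

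**Step 1: the algebra.** Let pL and pT be abstinence among observed ID/LAB and TAU patients, and mL and mT the missing proportions.

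- All non-abstinent (the main rule): RD = (1 - mL)pL - (1 - mT)pT.
- All abstinent: RD = (1 - mL)pL + mL - (1 - mT)pT - mT, which is the main RD + (mL - mT).
- Least favourable to ID/LAB (ID/LAB missing non-abstinent, TAU missing abstinent): RD = (1 - mL)pL - (1 - mT)pT - mT, which is the main RD - mT.

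On the rate-difference scale, the all-abstinent run therefore moves the estimate only by the difference in missing proportions.

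**Step 2: numbers.** One visit, 100 per arm, observed 60% v 40%. Tests are pooled two-proportion z-tests, z = (difference)/sqrt(2p(1 - p)/100), with p the mean of the two rates.

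| Loss, ID/LAB v TAU | All non-abstinent (main rule) | All abstinent | Least favourable to ID/LAB |
|---|---|---|---|
| 10% v 10% | 54 v 36, +18 | 64 v 46, +18 | 54 v 46, +8, p=0.26 |
| 20% v 20% | 48 v 32, +16, p=0.021 | 68 v 52, +16, p=0.021 | 48 v 52, -4, p=0.57 |
| 30% v 30% | 42 v 28, +14 | 72 v 58, +14 | 42 v 58, -16, p=0.024 |
| 15% v 30% | 51 v 28, +23, p=0.0009 | 66 v 58, +8, p=0.24 | 51 v 58, -7, p=0.32 |

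At 20% equal loss the opposite extreme is 68 v 32, or +36. At 15% v 30% it is 66 v 28, or +38.

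**Step 3: where the result tips.** Take 20% equal loss and keep all missing ID/LAB patients non-abstinent. With 2 of the 20 missing TAU patients abstinent the comparison is 48 v 34 (+14, p=0.044). With 4 of 20 it is 48 v 36 (+12, p=0.086). Significance is lost between these two.

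**Step 4: the planned scale.** The model uses a logit link, so the odds ratio matters. At 60% v 40% and 20% equal loss, both runs give OR 1.96, but only because 60 and 40 are symmetric about 50. At 30% v 15% observed and 20% equal loss:

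- All non-abstinent: 24 v 12, OR (0.24/0.76)/(0.12/0.88) = 2.32, p=0.027.
- All abstinent: 44 v 32, OR (0.44/0.56)/(0.32/0.68) = 1.67, p=0.080.

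The rate difference is 12 points in both, yet the conclusion changes. The least favourable case there is 24 v 32, or -8.

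**The case against.** The strongest reply is that the examples do more than the algebra suggests, and that they are only examples. Most of this stands.

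- **Unequal loss.** The plan does not assume equal loss. When TAU loses more patients, the main rule flatters ID/LAB and the all-abstinent run exposes it: +23 falls to +8 at 15% v 30% loss. Even at 20% v 25%, 48 v 30 (+18, p=0.009) becomes 68 v 55 (+13, p=0.059).
- **Scale.** On the planned logit scale the result can change with equal loss, as step 4 shows.
- **Open wording.** The plan commits to several methods and introduces the pair as instances. Multiple imputation or a tipping-point analysis would fit within the present text.
- **Overlap.** The main rule speaks of patients who cannot be located, the sensitivity sentence of missing weeks. If isolated missed visits by reachable patients were handled otherwise in the main analysis, the repetition would be incomplete. The plan describes no other handling for these outcomes.

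A reader might infer from the algebra that the check is void, or that it agrees whatever the missing patients did. The first two points rule that out. A reader might also see a contradiction in treating WHOQOL-Bref and PEG data as missing at random while presuming relapse for substance use. The plan limits the relapse assumption to substance-use outcomes, and presumed relapse alone does not make the other data missing not at random once earlier observations are in the model.

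The reply leaves one gap: no arm-specific analysis is named, so whether to run one, and in what form, could be decided after the data are seen.

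**Conclusion.** The point holds as a limited, inexpensive improvement to a secondary analysis. For abstinence, the two examples supply one new scenario. That scenario is a real but partial check, weakest when loss is similar in the two arms, and neither example lets missing patients differ by arm. The pair can therefore miss a change of sign: by the working above, +16 and +16 against -4 at 20% equal loss, and +23 and +8 against -7 at 15% v 30%. In those two cases the reversed difference is not itself significant; at 30% equal loss it is.

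A reader might go further and conclude that a fragile abstinence result would be reported as robust. The documents do not support that, because the list of methods is open and the all-abstinent run can itself overturn a result.

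The sizes rest on assumed abstinence and loss rates, a single visit and a crude z-test; they do not fit the planned longitudinal model. The least favourable case is a deliberate bound, not a forecast.

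**What to change.** In section 12.0, Intent to Treat, Dropouts, and Missing Data, for the substance-use outcomes:

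1. Keep the all-abstinent run.
2. Stop listing all non-abstinent as a separate sensitivity analysis, since it is the main rule.
3. Add multiple imputation within arm under missing at random, using baseline and earlier visits.
4. Add an arm-specific tipping-point grid, fitted with the planned logit-link longitudinal model. Vary the abstinence probability among missing ID/LAB and missing TAU patients separately, include the case least favourable to ID/LAB, and report where the 95% confidence interval first includes no difference.

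Arm-specific delta-adjusted imputation for WHOQOL-Bref and PEG is an optional extension, not the correction of an error.

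The cost is SAP wording and some extra analysis; no new data are needed. The downside is that a positive secondary result may look less robust.
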